1.0. Introduction

1.1. Overview

Early and longitudinal involvement of palliative care (PC) in the outpatient management of patients with advanced cancer improves patient-reported and end of life (EOL) care outcomes. While recommended by national organizations as the standard of care, this early integrated care model utilizes substantial PC resources, which has limited its dissemination across care settings. We seek to perform a multi-site randomized trial of stepped PC versus early integrated PC in patients with advanced lung cancer. By demonstrating the non-inferiority of a stepped PC model to early integrated PC, we seek to define a role for this more accessible, scalable and patient-centered approach to PC.

1.2. Background and Rationale

Early Integrated PC Improves Patient-Reported and End-of-Life Care Outcomes

Over the past decade, a growing body of evidence has supported a new role for PC clinicians in the outpatient management of patients with advanced cancer.¹⁻⁸ For example, Bakitas conducted a randomized trial comparing a telephone-administered PC psycho-educational intervention with usual care in patients with newly diagnosed poor prognosis cancers, which demonstrated improvements in quality of life (QOL) and mood.² In two additional trials, investigators evaluated in-person interventions administered by PC-trained clinicians. Specifically, Zimmermann evaluated a four-month intervention involving monthly outpatient PC visits in patients with poor prognosis cancers, demonstrating improvements in QOL, symptom burden and satisfaction, compared with usual care.⁵ Similarly, in our trial of patients with newly diagnosed advanced non-small cell lung cancer (NSCLC), monthly visits with PC throughout the course of illness (“early integrated PC”) improved patient-reported QOL and depression, compared with usual care.⁶ Notably, this study also demonstrated improvements in the delivery of EOL care with early integrated PC including greater documentation of EOL care preferences, longer length of stay in hospice, and less chemotherapy administration near death.⁹ More recently, we completed a larger efficacy trial of the early integrated PC model in patients with advanced cancers, which confirmed prior findings and also demonstrated that the intervention led to an increase in patient-clinician communication about EOL care preferences.¹⁰ While both telephone-based and brief duration in-person PC interventions improve patient-reported outcomes, only early integrated PC enhances communication and decision-making about EOL care.

Few Cancer Care Settings Can Deliver Guideline-Concordant Early Integrated PC

Based largely on the data described above, in 2012 and 2016 the American Society of Clinical Oncology (ASCO) published Clinical Oncology Practice Guidelines recommending early PC for any patient with advanced cancer.^{11,12} Similarly, the Institute of Medicine and the National Comprehensive Cancer Network recommend consideration of early PC for patients with advanced cancers.^{13,14} By recognizing the value of PC in the care of patients with advanced cancer, these recommendations represent a significant advance in the field of oncology. However, few institutions have sufficient numbers of PC clinicians to provide care in accordance with these guidelines.¹⁵ Despite a recent growth in the number of PC clinicians, data suggest that the current workforce would need to be at least tripled to meet the growing demand for their services.¹⁶ Moreover, it is

unlikely that there will ever be a sufficient number of trained PC clinicians to see all patients with advanced cancer from the time of diagnosis and throughout the course of illness.^{17,18} Thus, we must develop and evaluate health care delivery models that increase access to care and efficient utilization of PC services.

Stepped Care Increases Access with Limited Health Care Clinicians and Resources

Stepped care was initially developed as a health care delivery model to increase access to and efficiency of psychological therapy due to limited numbers of trained mental health clinicians.¹⁹ In stepped care, all patients receive care for their condition, but with a minimum of required contact with the specialty trained clinician.²⁰ More intensive treatment with the clinician is reserved for those who do not benefit sufficiently from the less intensive treatments. A key element of this model is that patients must be monitored systematically and “stepped up” to more intensive treatment if the minimal level of exposure to the clinician does not achieve sufficient health gain. Stepped care models have been shown to be effective in managing psychological illnesses such as depression, bulimia, and addiction as well as physical conditions including obesity, hypertension, and back pain.²¹⁻²⁴ Moreover, studies support the use of stepped care models to address psychological distress in patients with cancer.²⁵⁻²⁷ When compared with proven strategies of more intensive specialist-delivered treatment, stepped care can achieve similar outcomes using fewer resources and at a lower cost.^{22,28,29}

Stepped Care as a Strategy to Deliver Accessible and Patient-Centered PC

Stepped care is an appealing approach for PC delivery as it would enable all patients with advanced cancer to have some exposure to PC clinicians, thus representing guideline-concordant care. Importantly, stepped care is patient-centered in tailoring the delivery of PC services to patients’ clinical needs. Such a patient-centered approach to integrating palliative and oncology care is quite timely as cancer therapies are becoming more personalized and effective with fewer side effects. For example, patients treated with targeted oral chemotherapies often remain on treatment for years and may see their oncologist only every few months.^{30,31} While these patients may have challenges with the physical and psychological burdens of their cancer, many are unlikely to require monthly visits with a specialized PC clinician.^{32,33} Thus, in the modern era of cancer therapeutics, a stepped care model, in which low intensity PC is delivered to all patients at clinically relevant points when they are likely to have symptoms or concerns about their cancer while reserving a higher level of PC involvement when patients’ health worsens, may be more accessible, efficient, and patient-centered.

Lung Cancer is an Ideal Population in which to Study Patient-Centered PC

The strongest evidence base supporting early integrated PC is among patients with advanced lung cancer, with two randomized trials demonstrating significant improvements in QOL, mood, and EOL care.^{6,34} However, treatment paradigms for patients with advanced lung cancer are changing rapidly.³⁵ Approximately one-third of patients with metastatic lung cancer have gene mutations or fusions that predict responses to targeted oral therapies or express PDL1 and have tumor shrinkage with immune checkpoint inhibitors, both of which can portend a prognosis of several years.³⁶⁻⁴¹ Despite these advances, the majority of patients with advanced lung cancer do not respond to

novel therapies and have a median survival of approximately one year.⁴² Moreover, these patients often experience a high symptom burden and poor QOL at diagnosis, which intensifies throughout their illness course.⁴³ With the myriad of medical and psychosocial concerns that patients with advanced lung cancer experience, a one-size-fits-all approach to PC is unlikely to be optimal for this population. Rather, a PC delivery model personalized to each patient's disease course and care needs represents a more patient-centered approach for those with advanced lung cancer.

Scientific Premise of the Project

Early integrated PC has been shown to be an effective care model but is resource intensive, which has limited its dissemination in the outpatient oncology setting. Similarly, an insufficient number of trained clinicians has been a longstanding challenge in psychiatry, which led to the development of stepped care models to tailor treatment to the individual patient, ensure access to care, and increase efficiency. Although stepped care has not been specifically tested as a model for delivering PC, it has been used successfully in addressing the psychosocial needs of patients with cancer.^{25-27,44} In addition to increasing access to PC, a stepped care model is a more patient-centered approach by personalizing care to the patients' illness trajectory and needs. Importantly, a limitation of prior research regarding stepped care models is the inclusion of usual care as the control arm in clinical trials. To ensure a stepped care intervention is *as effective* as more resource intensive standard of care interventions requires a non-inferiority study design.¹⁹ Thus, we propose to perform a multi-site randomized trial of stepped PC versus early integrated PC in patients with advanced lung cancer. By demonstrating the non-inferiority of a stepped PC model to early integrated PC, we seek to define a role for this more accessible, scalable and patient-centered approach to PC.

2.0. Objectives

2.1. Primary Aim

To determine whether stepped PC is non-inferior to early integrated PC in improving patients' QOL at 24 weeks

Hypothesis: Patients assigned to stepped PC will report QOL that is non-inferior to patients receiving early integrated PC at 24 weeks.

2.2. Secondary Aims

A. To assess whether stepped PC is non-inferior to early integrated PC with respect to patient-clinician communication about EOL care preferences and length of stay in hospice.

Hypothesis: Stepped PC will be non-inferior to early integrated PC in the rate by which patients communicate their EOL care preferences to their clinicians and with respect to patients' length of stay in hospice.

B. To compare the superiority of stepped PC versus early integrated PC with respect to resource utilization.

Hypothesis: Stepped PC will utilize fewer PC resources than early integrated PC.

3.0. Research Subject Selection

We will recruit 510 patients with advanced lung cancer receiving their care at Massachusetts General Hospital, Duke Cancer Center, or University of Pennsylvania Abramson Cancer Center to participate in a multi-center, non-inferiority randomized trial of stepped PC versus early integrated PC. Patients will be randomized in 1:1 fashion and stratified by site (MGH vs. Duke vs. Penn) and underlying diagnosis (NSCLC vs. small cell lung cancer and mesothelioma). As patients with NSCLC have a significantly better prognosis than those with small cell lung cancer or mesothelioma, we will stratify by the underlying diagnosis to ensure adequate and balanced representation between the two study groups.

3.1. Patient Eligibility Criteria

Inclusion Criteria:

The patient eligibility criteria will mirror those of our prior early PC studies in this patient population.

1. Diagnosed with advanced NSCLC, small cell lung cancer, or mesothelioma, being treated with non-curative intent, and informed of advanced disease within the prior twelve weeks
2. Eastern Cooperative Oncology Group (ECOG) Performance Status from 0 (asymptomatic) to 2 (symptomatic and in bed <50% of the day)
3. The ability to read and respond to questions in English or Spanish
4. Primary cancer care at one of the three participating sites
5. Age ≥ 18 years

Exclusion Criteria:

Patients will be excluded if:

1. They are already receiving outpatient PC or hospice services since diagnosis of advanced NSCLC, small cell lung cancer, or mesothelioma
2. They have cognitive or psychiatric conditions as determined by the treating oncologist to prohibit study consent or participation

4.0. Research Subject Entry

4.1. Patient Screening

At all three sites, the study staff will screen all patients presenting to the outpatient thoracic oncology clinic for study participation. By reviewing the electronic scheduling system and health record to determine cancer stage and treatment goals, the study staff will identify all patients with advanced lung cancer who are not being treated with curative intent. This determination will be made based upon stage of disease and the designated treatment goal in the chemotherapy treatment plan as some patients with locally advanced disease cannot be treated for cure and some patients with metastatic disease are treated with curative intent. We will complete a privacy waiver with our protocol submissions to the Institutional Review Board (IRB) to allow study staff to screen the thoracic oncology clinic schedules and identify patients for study participation. We will institute the same patient screening procedures in all three of the participating thoracic oncology clinics.

4.2. Patient Recruitment

We will use the same recruitment and enrollment procedures used in our previous and ongoing trials.^{6,34} Prior to the study start, site investigators will meet with their respective thoracic oncology teams to review recruitment and enrollment procedures. Specifically, the study staff will send an email (see appendix) to the oncology clinicians to notify them when their patients appear to be eligible for study participation. If an oncology clinician reports that the patient is being treated with curative intent or otherwise does not meet eligibility criteria, study staff will document the reason.

4.3. Informed Consent Process

Either study staff or the oncology clinician can review the study details, offer study participation, and obtain informed consent in-person or verbally. Both the written and the verbal consent forms describe all study procedures, information about potential risks and benefits of participation, and information regarding who they can contact for further questions. The forms also state that participation is voluntary, that participants can refuse to answer any questions, that they can withdraw from the study at any time, and that study participation is in no way related to their medical care. Study participants who do not provide consent will be asked the reason why they prefer to not participate in the study.

4.3.1. In-Person Informed Consent Process

Willing participants will be presented with a detailed, HIPAA-compliant consent form and given the opportunity to sign written informed consent either with the study staff or their oncology clinician.

Patients who speak Spanish will have all study procedures and information regarding risks, benefits and study contacts explained to them verbally via the use of an interpreter or a Spanish-speaking study staff member as a first preference, or a family member as a second preference. Spanish speaking participants will be given the DF/HCC Spanish consent short form for signing, as well as a copy of the full English consent form for their own reference. The Spanish consent short form will be signed by the participant and by a witness. The witness will be either an interpreter, a Spanish-speaking study staff member or a family member. Spanish speaking participants will be provided with Spanish-version baseline demographic and study questionnaires.

4.3.2. Verbal Informed Consent Process

We are requesting a Waiver of Written Documentation of Consent. This study meets the requirements for a waiver as it is a Minimal Risk study and all study procedures can be communicated verbally. This Waiver will allow study staff to recruit participants remotely to address barriers to study enrollment including infrequent in-person visits, lack of space in clinic, and patients' time constraints. All patients who provide verbal consent will receive an unsigned copy of the written informed consent.

The study staff or an oncology clinician may contact eligible, English speaking patients to obtain verbal consent using the HIPAA-compliant verbal consent form. The verbal

consent process may be offered to patients via telephone or during a scheduled oncology video visit via institution-approved video technology. Verbal consent procedures will not apply to Spanish speaking patients. If the patient does not answer the phone, the clinician or study staff may leave a voicemail (see appendix 9.2 for suggested language for the voicemail).

4.4. Baseline Completion and Registration

Patients will be asked to complete baseline demographic and study questionnaires in-person, over the phone, or via institution-approved video technology with a study staff member at the time of consent, or alternatively via email, telephone, institution-approved video, or mail within two weeks of signing consent. Once baseline measures are complete, patients will be registered for study randomization.

If additional information about palliative care is requested by the patient, the study staff member or clinician may provide any of the following brochures about palliative care: an institutionally approved palliative care brochure produced by the site; the National Institute of Nursing Research brochure *“Palliative Care: The Relief You Need When You Have a Serious Illness”*; or the Center to Advance Palliative Care brochure *“Palliative Care: What You Should Know”*. These brochures are intended to provide additional information for potential study participants who are interested in learning more about palliative care.

DF/HCC institutions will register eligible participants in the Clinical Trials Management System (CTMS) Oncore as required by DF/HCC SOP REGIST-101. Registration must occur prior to the initiation of protocol-specific procedures.

For registration of patients from DF/HCC institutions, study staff will complete the protocol-specific eligibility checklist using the eligibility assessment documented in the participant’s medical record and/or research chart. Study staff will confirm that the participant meets all inclusion criteria as described in this protocol and the criteria on the eligibility checklist.

Patients from other investigative sites will be entered on the study centrally by MGH study staff. Study staff from the participating institution will confirm eligibility criteria and fax or email the following documents to study staff at MGH: deidentified signed consent form/s, copy of baseline assessment, and a completed eligibility checklist. MGH study staff will follow DF/HCC Standard Operating Procedure for Human Subject Research Titled *Subject Protocol Registration* (SOP #: REGIST-101) and register the participant on the protocol. Once the patient has been registered, a member of the MGH study staff (independent from study staff who recruit, enroll and administer assessments to participants) will perform randomization procedures using a computer-generated randomization schema, stratified by study site. MGH study staff will fax or e-mail the information about randomization to the study staff at the participating site. MGH study staff may also call the study staff at the participating site to verbally confirm registration and randomization.

5.0. Study Design and Methods

5.1. Study Design

We will conduct a randomized trial of stepped PC versus early integrated PC in patients with advanced lung cancer. We have chosen three specific aims focused on demonstrating the non-inferiority of the more accessible and patient-centered stepped care model.

5.2. Selection of Instruments

We selected instruments based on our prior studies and the theoretical framework of our intervention, which seeks to improve patients' QOL, illness understanding, use of adaptive coping strategies and ultimately communication and delivery of EOL care. Study staff will administer study assessments at baseline and multiple follow-up time points (with a +/- two-week window) to accommodate patient schedules (see Table 1). The selected self-report measures have strong psychometric properties and have been well validated in previous studies. All study measures are available in both English and Spanish, except the Self-Administered Comorbidity Questionnaire and the Prognosis and Treatment Perceptions Questionnaire, which were translated (forward and backward) into Spanish with a native Spanish speaking clinician.

Measures:

Demographic Questionnaire: Participants will self-report their gender, race/ethnicity, marital status, religion, education level, employment status, tobacco use, travel time and transportation mode to the cancer center, and health insurance co-payment charge.

Self-Administered Comorbidity Questionnaire (SCQ): Medical comorbidity will be assessed at baseline with the Self-Administered Comorbidity Questionnaire.⁴⁵ Patients will report on the presence of twelve comorbidities such as heart disease, lung disease, diabetes and arthritis. They will also have the option of reporting up to three further unlisted comorbidities and will be assigned a comorbidity score ranging from 0-45.

Functional Assessment of Cancer Therapy-Lung (FACT-L): The FACT-L is a 35-item QOL tool that assesses physical, social/family, emotional, and functional well-being, as well as lung cancer specific symptoms over the past 7 days.⁴⁶ We have used this measure in three prior PC trials in patients with lung cancer, demonstrating that early involvement of PC improves FACT-L scores.^{6,10}

EuroQol-5 Dimension (EQ-5D): The EQ-5D measures five dimensions of health (mobility, self-care, usual activities, pain/discomfort, and anxiety/depression) with three levels of severity and self-rated health status on a 0-100 visual analog scale^{47,48} and is sensitive to QOL changes in patients with lung cancer.^{47,49}

Patient Health Questionnaire-9 (PHQ-9): The PHQ-9 is a nine-item measure that evaluates symptoms of major depressive disorder according to the criteria of the *Diagnostic and Statistical Manual of Mental Disorders*, which can be scored continuously or categorically.⁵⁰ In our previous trials, early involvement of PC has improved PHQ-9 scores.^{6,10}

Brief Cope: The Brief Cope is a 28-item questionnaire that assesses methods of coping (e.g., active, acceptance, denial) using a 4-point Likert scale ranging from 1 “a lot” to 4 “never.”⁵¹ The psychometric properties of the Brief Cope have been demonstrated in studies of patients with serious illness and cancer.^{51,52} For our prior study, to minimize questionnaire burden, we solicited feedback from our research and PC teams about the coping strategies most likely to be influenced by our early PC intervention. We chose to exclude items such as self-distraction, substance use, and venting. We will limit our evaluation to eight coping strategies (16-items) deemed most relevant for the study (i.e., emotional support, positive reframing, active coping, acceptance, self-blame, denial, spiritual coping and behavioral disengagement). In our prior study, early involvement of PC increased use of active coping and decreased use of poor coping. We will administer 16-items in the current trial.

Support Service Utilization: At the 24-week primary endpoint, patients will be administered a single item assessing mental healthcare utilization since diagnosis. This item is designed to capture information which is routinely missing from the health record, as patients often either see mental health services external to the hospital, or access services which do not routinely document encounters in the electronic health record (EHR).

Prognosis and Treatment Perceptions Questionnaire (PTPQ): The PTPQ is a tool that assesses patients’ illness understanding, communication about prognosis and goals of care, as well as discussions and preferences regarding EOL care.⁵³ The PTPQ includes the item: “Have you discussed any particular wishes you have about the care you would want to receive if you were dying?” (Yes/No). This item has been previously used to assess EOL communication in patient with cancer.⁵⁴

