We recently found that improvements in QOL and depression with PC are mediated through use of adaptive coping skills, and prior studies have shown that age, gender, and race can moderate the impact of PC in patients with cancer.^{63,64} Therefore, we will conduct bootstrapped tests of mediation to determine whether group differences in the FACT-L are mediated by improved coping or other potential mediators such as psychological distress. Additionally, we will explore potential moderators of the interventions to ensure generalizability and identify whether certain groups benefit more from one of the two PC models. We will create interaction terms for the linear regression and linear mixed models to examine whether differences in FACT-L are moderated by patient factors (e.g., age, gender, race, baseline distress), disease or treatment factors, or study site.

The secondary aim of the study is to assess whether stepped PC is non-inferior to early integrated PC with respect to patient-clinician communication about EOL care preferences and length of stay in hospice. We will examine patient report of discussing EOL care preference with their clinicians using the following item: “Have you and your doctors discussed any particular wishes you have about the care you would want to receive if you were dying?” Although patients will complete this measure repeatedly during the course of the study, we will use the patient’s final assessment for this analysis. We will assess differences between study arms in the rate of patients reporting “yes” to this item using a one-sided alpha of 0.05 and a non-inferiority margin of 10%. The difference in rates between study arms will be assessed using a generalized linear regression model specified with an identity link function and binomial response probability distribution with adjustment for the randomization stratification factors and any demographic and clinical variables that are imbalanced between groups.

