## 6. Outcome Measures

Outcome data included self-report questionnaires collected prior to randomization (baseline) and then again at weeks 12, 24, 36 and 48 (with a  $\pm 2$ -week window) (see Table 1), as well as information collected from the EHR.

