**Table 1. Study Questionnaires**

Self-report measure	Baseline	Every 6 weeks	Weeks 12, 24, 36 & 48	Scoring
Demographics	X			n/a
SCQ	X			Range: 0-45 (higher is worse medical condition)
FACT-L	X	X 	X	Range: 0-136 (higher is better QOL)
PHQ-9	X		X	Range: 0-27 (higher is worse depression)
PTPQ	X		X	n/a

Brief Cope	X		X	Range: 2-8 for each facet (higher is more engagement in coping style)
EQ-5D	X		X	VAS Range: 0-100 (higher is better health state)
Support Service Utilization Item			X 	

 Step 1 patients completed FACT-L every 6 weeks for up to 18 months from enrollment.

 Collected only at week 24.

EQ-5D, EuroQol—5 Dimension; FACT-L, Functional Assessment of Cancer Therapy-Lung; PHQ-9, Patient Health Questionnaire-9; PTPQ, Prognosis and Treatment Perceptions Questionnaire; SCQ, Self-administered Comorbidity Questionnaire.

The primary outcome is patient-reported quality of life at 24 weeks from enrollment, as measured by the FACT-L.

The secondary outcomes are:

1. Patient report of patient-clinician communication about EOL care preference using the following item on the PTPQ: “Have you and your doctors discussed any particular wishes you have about the care you would want to receive if you were dying?” analyzed as “yes” versus “no.” The patient’s final assessment will be used.
2. Length of stay on hospice (in days) among patients who die during the study, as documented in the EHR.
3. PC resource utilization; specifically, the number of outpatient PC visits per patient during the study, as documented in the EHR.

The exploratory outcomes are:

1. Rate of change in quality of life from baseline to week 48, as measured by the FACT-L.
2. Cost-effectiveness as assessed by costs relative to quality adjusted life years. **Note:** Plans for the analysis of cost-effectiveness are not described in this SAP.
3. Patient-reported coping strategies at week 24, as measured by eight subscales of the Brief Cope, including subscales measuring emotional support, positive reframing, active coping, acceptance, self-blame, denial, spiritual coping, and behavioral disengagement, as well as higher-order factors reflecting active coping and avoidant coping).
4. Patient-reported prognostic understanding at week 24, based on relevant items on the PTPQ, including:
  - a. Patient’s primary goal of current cancer care. Responses will be dichotomized based on whether the patient selected “to cure my cancer” versus any of the other options.

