#### *Secondary Outcomes*

The difference between groups in the rate of patient-clinician communication about EOL care preference at the final follow-up assessment will be assessed using a generalized linear regression model specified with an identity link function and binomial response probability distribution. The model will include group assignment (stepped PC vs early integrated PC) and randomization stratification factors as main effects. Using the pre-specified non-inferiority margin of 10%, the nominal p-value for non-inferiority will be calculated using a one-sided test of the estimated difference in rates against a null value of -10%. Non-inferiority of stepped PC will be established if the nominal p-value is significant after application of the multiplicity adjustment procedure for secondary outcomes. Model-based estimates of the rate with 95% CI in each group, the difference in rates between groups and its 90% CI, the nominal p-value, and the multiplicity-adjusted p-value will be reported.

The difference between groups in the mean length of stay in hospice among patients who die during the study will be assessed using a linear regression model with main effects for group assignment (stepped PC vs early integrated PC) and randomization stratification factors. Using the pre-specified non-inferiority margin of 7 days, the nominal p-value for non-inferiority will be calculated using a one-sided test of the estimated difference in rates against a null value of -7. Non-inferiority of stepped PC will be established if the nominal p-value is significant after application of the multiplicity adjustment procedure for secondary outcomes. Model-based estimates of the mean with 95% CI in each group, the difference in means between groups and its 90% CI, the nominal p-value, and the multiplicity-adjusted p-value will be reported.

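### Secondary outcome 1 (EOL communication): two of its three definitions do not exclude the pre-randomization answer, and counting that answer would favour non-inferiority

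*Protocol*

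**What the plan says.** Secondary outcome 1 carries a formal non-inferiority claim. Protocol 7.4 plans it with 510 patients, a 30% rate in early integrated PC, a 10-point margin, one-sided 0.05 and more than 80% power. SAP 9 tests it with an identity-link binomial model against −10%, subject to the Benjamini-Hochberg rule at an FDR of 0.15.

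**Which answer counts.**
- Protocol 7.5, after noting that the item is asked repeatedly: "we will use the patient’s final assessment for this analysis".
- SAP 6, outcome definition: "The patient’s final assessment will be used".
- SAP 9, model description: "communication about EOL care preference at the final follow-up assessment".

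The assessment tables in both documents schedule the PTPQ at baseline. Protocol 4.4 and SAP 4 require complete baseline measures before randomization. SAP 6 opens with "Outcome data included self-report questionnaires collected prior to randomization (baseline) and then again at weeks 12, 24, 36 and 48". Item 2 of the SAP addendum sets a post-baseline rule for a different PTPQ outcome, prognostic understanding (exploratory outcome 4), and does not mention this one.

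**Item wording.** Protocol 5.2 gives the item as "Have you discussed any particular wishes you have about the care you would want to receive if you were dying". Protocol 7.5 and SAP 6 give it as "Have you and your doctors discussed any particular wishes you have about the care you would want to receive if you were dying".

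**The concern.** Only the SAP 9 phrase excludes a pre-randomization answer. Take a patient who answered yes at baseline and returned no later PTPQ: under Protocol 7.5 and SAP 6, read literally, the outcome is yes; under SAP 9 it is missing. A patient who answered no at baseline and returned nothing later is a no under the first rule and missing under the second. The denominator and the estimate both depend on which text the analyst follows, and SAP 2 describes the trial as unblinded.

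The choice is not neutral. Care that has not yet started cannot affect a baseline answer. Adding such answers in similar numbers to both arms pulls the observed difference toward zero, and in a non-inferiority test that favours the claim.

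The item wording is a smaller, separate matter. If the form given to patients does not name doctors, a yes does not show that a clinician was involved.

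**Working it through.** **Inputs from the documents.** 255 per arm (510, 1:1); 30% in early integrated PC; margin 10 points; one-sided 0.05 (z = 1.645). At the margin, stepped PC is therefore at 20%.

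**Inputs assumed.** m, the share with no post-baseline PTPQ answer, taken as equal in both arms; b, the baseline yes rate among those patients, equal in both arms at 10–20%. Neither is in the documents. The 35% in Protocol 7.4 is missingness at week 24. A patient absent then may have answered at week 12, so I do not use 35% as m.

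**The plan's own power.** At true equality, with unpooled variance:

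SE = √(2 × 0.30 × 0.70 / 255) = 0.0406; power = Φ(0.10/0.0406 − 1.645) = Φ(0.819) = 79.4%.

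With the null variance taken at 30% and 20%, power is 82.1%. The unpooled formula needs 260 per arm for 80%. The stated figure is thus reproduced closely, but only if all 510 patients supply an answer.

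**Baseline answers counted, truth at the margin.** The expected rates are

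p_I = (1 − m) × 0.30 + m × b and p_S = (1 − m) × 0.20 + m × b,

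so the expected deficit is 0.10 × (1 − m). The chance of declaring non-inferiority is

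Φ[(0.10 − 0.10(1 − m))/SE − 1.645], with SE = √{[p_I(1 − p_I) + p_S(1 − p_S)]/255}.

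Example, m = 10% and b = 10%: p_I = 0.28, p_S = 0.19, SE = √(0.3555/255) = 0.0373; Φ(0.010/0.0373 − 1.645) = Φ(−1.377) = 8.4%.

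| m | Expected deficit | False non-inferiority (b = 10% to 20%) |
|---|---|---|
| 0 | 10.0 points | 5.0% |
| 5% | 9.5 | 6.5% |
| 10% | 9.0 | 8.4% |
| 20% | 8.0 | 13.6% to 13.3% |

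**If m differs by arm.** The expected deficit is 0.10 − m_I(0.30 − b) + m_S(0.20 − b). With b = 10% this is 0.10 − 0.20 m_I + 0.10 m_S, which is below 0.10 unless m_S is more than twice m_I. With b = 20% it is 0.10 − 0.10 m_I, which is always below 0.10 when m_I is above zero. The direction therefore does not need exactly equal loss.

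**Post-baseline answers only, true equality.** Power = Φ[0.10/√(0.42/n) − 1.645]:

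| Lacking follow-up | n per arm | Power |
|---|---|---|
| 5% | 242 | 77.5% |
| 10% | 229 | 75.5% |
| 20% | 204 | 71.2% |

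These are two-sample approximations without the stratification factors, at nominal 0.05. With three secondary tests, the Benjamini-Hochberg thresholds are 0.05, 0.10 and 0.15 for the smallest, middle and largest p-value. At m = 10% and b = 15%, the chance of passing a threshold of 0.10 is 15.5% instead of 10%, and of passing 0.15 about 22% instead of 15%.

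**The case against.** The best defence is that SAP 9 specifies the test and says follow-up, so the shorter phrases in SAP 6 and Protocol 7.5 are shorthand. The opening of SAP 6 need not make baseline an outcome, since it introduces a table that also lists baseline-only items such as demographics. Using a baseline answer would also sit badly with the SAP 8 rule of analysing available data without imputation. Addendum item 2 can be read as showing that the team takes final to mean post-baseline.

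Much of this stands as a guess at intent, and a reader should not infer that the sponsor plans to count baseline answers. Nor does the power statement on all 510 show that: an omitted allowance for loss explains it equally well. But the outcome definition is where one looks to see what is scored, two of the three texts do not exclude baseline, and the addendum spelled out the restriction for a lower-ranked outcome only.

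On wording, a reader might infer that the shorter item in Protocol 5.2 also makes non-inferiority easier to claim. The documents do not support that. Both analysis definitions name doctors, so the shorter text matters only if the fielded form matches it. The direction is also open. Let h be the share of patients without a doctor discussion who talked to someone else. The observed deficit is then 0.10 + 0.70 h_I − 0.80 h_S. With h_S = 20%, it exceeds 10 points once h_I passes 0.16/0.70, about 23%. The visit content in Protocol Table 2 includes caregiver communication, so more such talk in the arm with more visits is plausible.

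**Conclusion.** The point holds for the choice of assessment. The documents give two rules for one formal non-inferiority outcome, and the literal form of one admits pre-randomization answers. If that form were followed, false non-inferiority at the margin would be about 6.5%, 8.4% or 13–14% for m of 5%, 10% or 20%, against 5%. The size rests on assumed m and b, on similar loss in the two arms, and on the nominal level before the FDR step; it is a range, not an estimate of what happened. Randomization makes baseline answers equal in expectation over all patients. Extending that to patients without follow-up is part of the assumption.

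The power statement needs correcting whichever way the text was meant, because it makes no allowance for patients without a follow-up answer once SAP 9 is followed.

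The wording difference is a minor documentation correction with no claimed direction of bias. The remaining question there is only whether the outcome's name fits the form.

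**What to change.** 1. In Protocol 7.5 and SAP 6, replace the rule with: *the last non-missing post-baseline (week 12–48) answer; patients with none are missing; the baseline answer is never used as the outcome.* This matches SAP 9, and a dated addendum item would suffice for the SAP.
2. Report by arm the number with no post-baseline answer, and restate the power in Protocol 7.4 for the number expected to have one.
3. Check the English and Spanish PTPQ as fielded and quote that wording in Protocol 5.2. If it does not name doctors, do not describe the outcome as patient-clinician communication.

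The cost is a few sentences and a look at the forms, with no new data. The real price is the smaller analysed number and the lower power shown above; if the form proves not to name doctors, the claim also narrows.
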